females) associated with T2D, but not a higher risk for bladder cancer [R15-4869]. Another Swedish inpatient register-based cohort indicated a higher risk of kidney cancer associated with T2D in both women (SIR = 1.7, 95% CI; 1.4-2.0) and men (SIR = 1.3; 95% CI; 1.1-1.6) throughout the duration of follow-up (1-25 years) [R10-6630]. Crude IRs of bladder cancer in patients with T2D range from 38 per 100,000 PY in women from Denmark [R12-1334] to 140-150 per 100,000 PY in men in Sweden and Denmark [R12-0368, R12-1334]. Meta-analyses of observational studies suggest that incidence of kidney cancer in patients with T2D is approximately 40% higher than that in the general population [R13-1812]. The available crude incidence estimates of renal cancer in men with T2D range between 40 and 50 per 100,000 PY in most studies.

Co-existence of hyperinsulinemia and hyperglycaemia in T2D and associated obesity may have a higher associated risk for cancers [R10-6494]. However, there may be additional risks from antidiabetic treatments and insulins, albeit these may be non-significant risks [R10-6494]. Other risk factors of urinary tract cancer are smoking amount and duration [R15-4868], different occupational and environmental exposures [R15-4865], history of kidney/ureter stones [R15-4863], sex, chronic bladder irritation and infections, genetics and family history, chemotherapy and radiation therapy [R15-4866; R15-4856].

6.1.1 Incidence of urinary tract malignancies in the study population in the UK and Sweden observed in the fifth interim report of this study

The country-specific IRs of urinary tract malignancies were estimated in the study population identified in the UK, Sweden and Finland, from 1st August 2014 to 31st December 2020 (2019 for Sweden).

In the UK CPRD GOLD, during a total of 147,020 patient years, 164 urinary tract cancer events were recorded in the study population with an incidence rate of 111.5 (95% CI, 95.7-130.0) per 100,000 patient years. The incidence rate of bladder cancer was 66.7 (95% CI, 54.7-81.2) per 100,000 patient years with a total of 98 events. For renal cancer, the incidence rate was 26.5 (95% CI, 19.4-36.3) per 100,000 patient years with a total of 39 events.

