8.5 STUDY SIZE

The study size will be driven by the uptake of empagliflozin and the primary comparator (DPP-4 inhibitors) in the UK, Sweden, and Finland. Originally, it was expected that by the end of 2019, approximately 18,000 empagliflozin-treated patients will accumulate in the CPRD and Swedish databases. However, based on the conservative estimates from the fifth interim analysis ([Annex 1](#)), the expected sample size is higher than anticipated. Taking into account the addition of Finland, the addition of CPRD Aurum, and the extension of the study period (end of 2020 for Sweden and Finland, end of 2021 for CPRD), a total of approximately 67,490 empagliflozin users are expected to be eligible for inclusion in the study ([Table 6](#)). However, the number of patients available for analysis may be lower. Given the observed patient numbers, it is expected that the maximum achievable matching ratios will be 1:3 for UK CPRD (GOLD and Aurum), 1:1 for Sweden, and 1:2 for Finland.

Table 6

Observed and expected number of patients eligible for inclusion in the study population, by study drug group (including fixed-dose combinations with metformin), by study country and overall, using an arithmetic growth assumption.

Year	Study drug group	Finland	Sweden	CPRD GOLD	CPRD Aurum ⁴	Pooled
2014 ¹	Empagliflozin	0	0	5		5
	DPP 4-inhibitors	5,824	3,214	2,555		11,593
	Other SGLT-2 inhibitors	127	662	683		1,472
2015 ¹	Empagliflozin	91	629	157		877
	DPP 4-inhibitors	14,130	10,305	6,851		31,286
	Other SGLT-2 inhibitors	320	1,537	2,065		3,922
2016 ¹	Empagliflozin	2,201	2,181	897		5,279
	DPP 4-inhibitors	11,391	12,126	5,648		29,165
	Other SGLT-2 inhibitors	1,463	1,183	1,740		4,386
2017 ¹	Empagliflozin	3,725	4,811	1,391		9,927
	DPP 4-inhibitors	7,402	13,677	4,577		25,656
	Other SGLT-2 inhibitors	1,475	1,191	1,493		4,159
2018 ¹	Empagliflozin	4,293	8,738	1,536		14,567
	DPP 4-inhibitors	6,959	12,798	4,158		23,915
	Other SGLT-2 inhibitors	1,610	1,030	1,470		4,110
2019 ¹	Empagliflozin	5,182	10,169	1,846		17,197
	DPP 4-inhibitors	6,158	11,673	3,622		21,453
	Other SGLT-2 inhibitors	1,853	1,061	1,665		4,579
2020 ²	Empagliflozin	2,777	5,806	1,541		10,124
	DPP 4-inhibitors	2,215	4,688	2,210		9,113
	Other SGLT-2 inhibitors	1,201	653	1,369		3,223
2021 ³	Empagliflozin			969		
	DPP 4-inhibitors			1,051		
	Other SGLT-2 inhibitors			726		
Total	Empagliflozin	18,269	32,334	8,342	8,545	67,490
	DPP 4-inhibitors	54,079	68,481	30,672	59,283	212,515

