Year	Study drug group	Finland	Sweden	CPRD GOLD	CPRD Aurum ⁴	Pooled
	Other SGLT-2 inhibitors	8,049	7,317	11,211	25,277	51,854

1 Observed number of patients.

2 Observed number of patients until 30th June for Sweden and Finland and until 31st December for UK CPRD GOLD, taking into account the extension of the study period to the end of 2021 for UK CPRD.

3 Expected number of patients (arithmetic growth assumption given observed numbers in previous years) between 1st January and 30th June, taking into account the 6 months minimum follow-up.

4 Only aggregate level data up (2014-2020) of was available for CPRD Aurum. Patient numbers were extrapolated based on assumptions derived from CPRD GOLD data, taking into account the extension of the study period to the end of 2021
DPP-4=dipeptidyl peptidase-4 inhibitors; SGLT-2=sodium glucose co-transporter-2 inhibitors; UK=the United Kingdom

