6.4. PROPENSITY SCORE MATCHED COHORTS

Matched full cohort

Propensity score matched cohorts will be derived in each country by matching each initiator of empagliflozin at index date with initiators of DPP-4 inhibitors at index date with a variable matching ratio up to 1:3 (1:1 in a sensitivity analysis) using greedy matching methods (cf. Section 6.5). Free or fixed dose combination use of metformin at index date will be used as an exact matching variable.

Matched metformin-user only cohort

Using the propensity scores computed using the entire cohort, a matched metformin-user only cohort will be derived by matching within a subgroup including only patients using metformin in free or fixed dose combination with the study drugs at index date. Each initiator of empagliflozin at index date will be matched with initiators of DPP-4 inhibitors at index date with a variable matching ratio up to 1:3 using greedy matching methods (cf. Section 6.5).

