6.5.2. Matching method

For matching the full cohort, concomitant use of metformin at index date will be an exact matching variable.

Matching will be carried out in several rounds to achieve the highest possible matching ratio given the available data in each country (up to 1:3 matching). In the first round of matching, for each empagliflozin initiator i_E with index date T_{i_E} , all individuals initiating DPP-4 inhibitors within 3 months (90 days) before or after T_{i_E} and with the same status of concomitant metformin use at T_{i_E} will be eligible as comparators. For UK CPRD data, only individuals from the same database (GOLD or Aurum) as the empagliflozin initiator will be considered as eligible comparators. Of these, the individual with the closest propensity score(s) to that of i_E within a predefined propensity score interval will be selected (Greedy matching method). In case of ties, the selection will be made randomly. After each round of selection, the selected comparators are then removed from the pool of possible comparators for further selection (sampling without replacement) [5].

The predefined propensity score interval will be calculated based on the standard deviation of the logit of propensity score δ multiplied by a coefficient k . The value of the coefficient k will be initially set to 0.2, i.e. using a caliper of 0.2 standard deviations (i.e. 0.2 δ). The coefficient k will then be calibrated to ensure at least 99% of empagliflozin initiators have matches from initiators of DPP-4 inhibitors after the first round of propensity score matching [6]. The same calibrated matching caliper $k\delta$ used in the first matching round will be reused in the second and third matching rounds.

Matching by time-period, based on index dates, enables better control of time-varying confounders including changing prescription patterns for empagliflozin and potential confounding. In case there is a strong time bias in the number of matches per empagliflozin user (e.g., initiators in early years have more matches than initiators from later years), a relaxation of the criteria for matching within time-period will be considered. In addition, the criteria for calibrating coefficient k may be modified if the data does not allow matching of 99% of empagliflozin initiators.

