6.7.3.1. META-ANALYSIS OF DESCRIPTIVE ANALYSES

Pooled incidence rates

For each outcome, the aggregated number of events and person-time at risk will be collected from all study countries to estimate the pooled IRs and their 95% CIs.

The pooled IRs for all K countries will be estimated as

$$IR_{pooled} = \frac{\sum_{k=1}^K x_k}{\sum_{k=1}^K t_k}$$

where x_k and t_k are the number of events and the person-time at risk in each country k .

95% CIs will be estimated using Poisson regression and reported similarly using Table 22.

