Hazard ratio estimates using adjusted model	
Using matched cohorts
 
Stratified by gender.
 
(18 tables, 3 outcomes x 2 strata by gender x 3 countries)
	As treated exposure definition	Main outcomes- Table 8	Table 25
Hazard ratio estimates using adjusted model	
Using matched cohorts
 
Stratified by insulin use at index.
 
(18 tables, 3 outcomes x 2 strata by insulin use at index x 3 countries)
	As treated exposure definition	Main outcomes- Table 8	Table 25
Meta-analyses for adjusted HR estimates	
Using adjusted HR estimates and 95% CIs from all study countries.
 
For each stratification variable listed above.
 
(54 figures, 3 outcomes x (3+4+7+2+2) strata)
	As treated exposure definition	Main outcomes- Table 8	Figure 8
Secondary objectives:				
Descriptive analysis				

Analysis	Details	Exposure definition	Outcomes	Template
Stratified incidence rates	Using matched cohorts Country specific analysis (9 tables, 3 outcomes x 3 countries)	Cumulative exposure dose of empaglifloz in	Main outcomes- Table 8	Table 30
Stratified incidence rates	Using empagliflozin users subgroup Country specific analysis (9 tables, 3 outcomes x 3 countries)	Empaglifloz in daily dose	Main outcomes- Table 8	Table 31
Stratified incidence rates	Using empagliflozin users subgroup Country specific analysis (9 tables, 3 outcomes x 3 countries)	Cumulative exposure duration to empaglifloz in	Main outcomes- Table 8	Table 32
Meta-analysis of incidence rates	Using pooled number of outcome events and person-time from all study countries (9 tables, 3 outcomes x 3 secondary exposure definitions)	The secondary exposure definitions listed above	Main outcomes- Table 8	Table 30- Table 32
Secondary objectives: Comparative analysis				
Hazard ratio estimates using adjusted model	Using matched cohorts Country specific analysis (9 tables, 3 outcomes x 3 countries)	Cumulative exposure dose of empaglifloz in	Main outcomes- Table 8	Table 26
Hazard ratio estimates using adjusted model	Using matched cohorts Country specific analysis (9 tables, 3 outcomes x 3 countries)	Empaglifloz in daily dose	Main outcomes- Table 8	Table 27

Analysis	Details	Exposure definition	Outcomes	Template
Hazard ratio estimates using adjusted model	Using matched cohorts Country specific analysis (9 tables, 3 outcomes x 3 countries)	Cumulative exposure duration to empagliflozin	Main outcomes- Table 8	Table 28

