Proprietary confidential information © 2024 Boehringer Ingelheim International GmbH or one or more of its affiliated companies

Table 22 Incidence rates per 1000 patient years of [Outcome name] with 95% confidence interval in the [Study country/pooled] matched cohort(s). The number of patients in each strata and the total number of person years are also presented.

Variable and strata	N Patients	N events	Person years	Rate	Lower 95% CI	Upper 95% CI
Absolute incidence						
Total	N	N	N	x.xx	x.xx	x.xx
Exposure category (As treated)						
Empagliflozin	N	N	N	x.xx	x.xx	x.xx
DPP-4 inhibitors	N	N	N	x.xx	x.xx	x.xx
Age at index (years)						
18-49	N	N	N	x.xx	x.xx	x.xx
50-64	N	N	N	x.xx	x.xx	x.xx
65-69	N	N	N	x.xx	x.xx	x.xx
70-74	N	N	N	x.xx	x.xx	x.xx
75-79	N	N	N	x.xx	x.xx	x.xx
80-84	N	N	N	x.xx	x.xx	x.xx
85 and over	N	N	N	x.xx	x.xx	x.xx
Sex						
Male	N	N	N	x.xx	x.xx	x.xx
Female	N	N	N	x.xx	x.xx	x.xx
Highest level of education						
Compulsory	N	N	N	x.xx	x.xx	x.xx
Upper secondary	N	N	N	x.xx	x.xx	x.xx
Post secondary	N	N	N	x.xx	x.xx	x.xx
Disposable income, individual						
< Q1	N	N	N	x.xx	x.xx	x.xx
Q1 – Q2	N	N	N	x.xx	x.xx	x.xx
Q2 – Q3	N	N	N	x.xx	x.xx	x.xx
≥ Q3	N	N	N	x.xx	x.xx	x.xx
Disposable income, family						
< Q1	N	N	N	x.xx	x.xx	x.xx
Q1 – Q2	N	N	N	x.xx	x.xx	x.xx
Q2 – Q3	N	N	N	x.xx	x.xx	x.xx
≥ Q3	N	N	N	x.xx	x.xx	x.xx

Proprietary confidential information © 2024 Boehringer Ingelheim International GmbH or one or more of its affiliated companies

Variable and strata	N Patients	N events	Person years	Rate	Lower 95% CI	Upper 95% CI
Marital status						
Registered partnership (incl. married)	N	N	N	x.xx	x.xx	x.xx
Widowed	N	N	N	x.xx	x.xx	x.xx
Separated	N	N	N	x.xx	x.xx	x.xx
Single	N	N	N	x.xx	x.xx	x.xx
Calendar year of index date						
2014	N	N	N	x.xx	x.xx	x.xx
2015	N	N	N	x.xx	x.xx	x.xx
2016	N	N	N	x.xx	x.xx	x.xx
2017	N	N	N	x.xx	x.xx	x.xx
2018	N	N	N	x.xx	x.xx	x.xx
2019	N	N	N	x.xx	x.xx	x.xx
2020	N	N	N	x.xx	x.xx	x.xx
Diabetes treatment complexity at index date						
Monotherapy	N	N	N	x.xx	x.xx	x.xx
Dual combination therapy	N	N	N	x.xx	x.xx	x.xx
Triple combination therapy	N	N	N	x.xx	x.xx	x.xx
Insulin use						
Yes	N	N	N	x.xx	x.xx	x.xx
No	N	N	N	x.xx	x.xx	x.xx
Metformin use						
Yes	N	N	N	x.xx	x.xx	x.xx
No	N	N	N	x.xx	x.xx	x.xx
Oral glucose lowering drugs use						
Yes	N	N	N	x.xx	x.xx	x.xx
No	N	N	N	x.xx	x.xx	x.xx
Sulfonylureas use						
Yes	N	N	N	x.xx	x.xx	x.xx
No	N	N	N	x.xx	x.xx	x.xx
Thiazolidinediones use						
Yes	N	N	N	x.xx	x.xx	x.xx

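### Pooling incidence rates across countries with different matching ratios makes the pooled empagliflozin rate about 1-10% higher than the DPP-4 rate when the drugs do not differ

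*SAP*

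**What the plan says.** SAP 6.7.3.1 defines the pooled IR for each outcome as summed events divided by summed person-time: "the aggregated number of events and person-time at risk will be collected from all study countries to estimate the pooled IRs". It gives no weighting or standardisation by country. The result goes into Table 22 of SAP Annex III, a template for both country and pooled results in which empagliflozin and DPP-4 inhibitors are adjacent rows. Table 30 sets never-exposed patients against cumulative-dose rows, and SAP 6.10 plans pooled versions of both tables.

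SAP 6.4 matches at a "variable matching ratio up to 1:3 (1:1 in a sensitivity analysis) using greedy matching methods". Protocol 8.5 expects that "the maximum achievable matching ratios will be 1:3 for UK CPRD (GOLD and Aurum), 1:1 for Sweden, and 1:2 for Finland". SAP 6.5.2 limits controls to those starting within 90 days of the empagliflozin patient. It foresees that "initiators in early years have more matches than initiators from later years", and says that relaxing the time criterion will then be considered.

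IRs by drug are part of each of the three primary objectives (protocol 7, SAP 2.2).

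**The concern.** Matching is done within country, so it balances the drugs inside each country but not the country mix between drugs. At the expected ratios the UK supplies 26% of empagliflozin person-years and 43% of DPP-4 person-years, and it has the lowest rate for all three outcomes. Adding across countries therefore mixes drug with country.

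The hazard ratio comes from within-country models, so the pooled rates can point away from it. With a true rate ratio of 0.90 in every country, the pooled urinary tract rates at the expected ratios would show 0.90 × 1.066 = 0.96. A reader who subtracts the two rows to get excess cases would find about 9 per 100,000 person-years when there are none.

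**Working it through.** **Inputs.**
- Expected empagliflozin initiators (protocol abstract, Table 6): UK 16,887; Sweden 32,334; Finland 18,269.
- Mean follow-up (protocol 8.5): 2.4, 2.2 and 2.4 years.
- IRs per 100,000 person-years for urinary tract/bladder/renal cancer: UK 111.5/66.7/26.5; Sweden 164.5/104.1/58.0; Finland 161.5/86.8/71.6.

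**The plan's own figures.** The documents give no pooled IR. The country rates reproduce from protocol 6.1.1. For the UK, "In the UK CPRD GOLD, during a total of 147,020 patient years, 164 urinary tract cancer events were recorded in the study population", and 164/147,020 = 111.5 per 100,000. Sweden is 346/210,329 = 164.5 and Finland 415/256,947 = 161.5.

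Table 7 power (HR 1.5, urinary tract) follows closely from Φ(√(km)·|HR−1|/(k·HR+1) − 1.96), where k = 1/r, r is the number of DPP-4 patients per empagliflozin patient, and m = N × (follow-up − 0.5) × IR × (HR + r). This gives Sweden 85.2% against 85.1% stated and Finland 80.8% against 80.6%. The fit needs the 6-month lag deducted, so the lag is applied in step 4. The UK figure does not reproduce from its footnote inputs (67.1% against 63.7%), but that does not affect this point.

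**Step 1: person-years.** Empagliflozin: 16,887 × 2.4 = 40,529; 32,334 × 2.2 = 71,135; 18,269 × 2.4 = 43,846; total 155,509 (shares 26/46/28%). DPP-4 at 3/1/2: 121,586; 71,135; 87,691; total 280,412 (UK 43%).

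**Step 2: pooled IRs with each country's rate applied to both drugs.**

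| Outcome | Expected events, empagliflozin / DPP-4 | Pooled IR, empagliflozin / DPP-4 | Ratio |
|---|---|---|---|
| Urinary tract | 233.0 / 394.2 | 149.8 / 140.6 | 1.066 |
| Bladder | 139.1 / 231.3 | 89.5 / 82.5 | 1.085 |
| Renal | 83.4 / 136.3 | 53.6 / 48.6 | 1.104 |

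With the 16,360 UK initiators of the table footnotes, the ratios are 1.065, 1.084 and 1.101. With one ratio in all countries they are 1.000.

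**Step 3: other matching ratios.** Capping each index year in Table 6 at 3 controls per empagliflozin initiator gives, for Sweden, 0 + 1,887 + 6,543 + 13,677 + 12,798 + 11,673 + 4,688 = 51,266, and 51,266/32,334 = 1.59. Finland is 29,610/18,269 = 1.62 and CPRD GOLD 18,391/8,342 = 2.20. Aurum has no yearly counts ("Only aggregate level data up (2014-2020) of was available for CPRD Aurum"), so three assumptions are shown. The last row drops the time window and uses Table 6 totals capped at 3: Sweden 68,481/32,334 = 2.12, Finland 54,079/18,269 = 2.96, UK 3.

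| Ratios UK / Sweden / Finland | Urinary tract | Bladder | Renal |
|---|---|---|---|
| 2.20 / 1.59 / 1.62 (Aurum like GOLD) | 1.024 | 1.024 | 1.047 |
| 2.61 / 1.59 / 1.62 (Aurum at 1:3) | 1.038 | 1.038 | 1.076 |
| 3 / 1.59 / 1.62 (whole UK at 1:3) | 1.050 | 1.050 | 1.103 |
| 3 / 2.12 / 2.96 (Table 6 totals) | 1.016 | 1.026 | 1.014 |

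**Step 4: against sampling error.** The standard error of the log rate ratio is √(1/e₁ + 1/e₂). With 0.5 year deducted from follow-up, expected events at 3/1/2 are 182.3/309.9, 108.8/181.7 and 65.2/107.1, with standard errors 0.093, 0.121 and 0.157. The excess is then 0.68, 0.67 and 0.63 standard errors. With no drug effect, the pooled empagliflozin rate would be the higher one in about 74-75% of studies instead of 50%. With Table 6 totals this falls to 54-59%. Without the lag deduction the expected-ratio figures are 0.71-0.77 standard errors and 76-78%.

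**Step 5: sensitivity.** The UK renal rate rests on 39 GOLD events (95% CI 19.4-36.3). At those limits the renal ratio at 3/1/2 runs from 1.14 to 1.06. If Aurum rates were 20% above or below GOLD (an assumption), the ratios at 3/1/2 are 1.050-1.083, 1.068-1.103 and 1.092-1.116.

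**The case against.** The strongest reply is that little depends on this table. It is descriptive, and no pooled rate ratio or test is planned. Drugs are compared through within-country hazard ratios combined by inverse variance (SAP 6.7.3.2), and the forest plots show events and IR by drug and country. SAP 6.7.3.2 also looks at variability in incidence rates before pooling. In Table 22 units the urinary tract difference is at most 1.50 against 1.41 per 1,000 person-years at the expected ratios, within a confidence interval of roughly ±13% on the empagliflozin rate (1.96/√233). The tilt is against the sponsor's drug, so it would not hide harm. All of this stands and keeps the point minor.

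The size can also be challenged. The 7-10% needs Sweden at 1:1, whereas Table 6 would support more, and SAP 6.5.2 allows the time window to be relaxed. That is why the range goes down to 1-3%. That lower end is a best case, because propensity-score and date restrictions will reduce the matches actually found.

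The planned 1:1 sensitivity analysis would remove the country-mix effect, but the readable SAP does not list IRs for it. Forest plots by country let a careful reader see the cause; they do not correct the pooled rows.

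A reader might infer that the pooled hazard ratio, and so the main safety conclusion, is biased in the same way. The documents do not support that: hazard ratios and country-level IRs are formed inside each country, where the mix cannot enter.

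**Conclusion.** The point holds for the crude pooled IRs only. With equal rates for both drugs in every country, the pooled empagliflozin rate is expected to be higher by 7-10% at the protocol's ratios, 2-10% at ratios capped by index year from Table 6, and 1-3% if Table 6 totals are the only limit. The direction is the same in every scenario tried, and only equal ratios bring it to zero. The shift is systematic but below sampling error: about 0.7 standard errors at most at the reported rates, with empagliflozin higher in about 54-75% of no-effect studies after the lag. The renal figure is the least certain (1.06-1.14 at the expected ratios).

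This rests on equal mean follow-up for the two drugs within a country and on GOLD rates applied to all UK patients. A reader might also infer that the table is likely to show a false signal by itself. At this size it is not. The harm is to how two adjacent rows are read, which makes this a low-priority but worthwhile change.

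**What to change.** In SAP 6.7.3.1 and the exposure rows of pooled Table 22, keep the crude pooled IRs and add country-standardised IRs with 95% CIs:

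- estimate: Σ w_k · x_k/t_k, with x_k events and t_k person-time for that drug in country k;
- variance: Σ w_k² · x_k/t_k²;
- w_k: one fixed set for both drugs, for example the person-time shares of the matched empagliflozin cohort (expected 26% UK, 46% Sweden, 28% Finland).

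With equal within-country rates both rows then read 149.8, 89.5 and 53.6 per 100,000 person-years.

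Do the same in Table 30 where counts allow. Renal dose rows will be sparse: 40,529 × 26.5/100,000 is about 11 UK renal cancers on empagliflozin over four rows. There the footnote alone is enough.

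The footnote should say two things: crude pooled rates are not comparable between drugs, and standardised rates remove country mix but not within-country differences that arise because some kinds of patients obtain more controls than others.

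The cost is a paragraph of SAP text and one extra set of columns. The events and person-time are aggregates the plan already collects, so no individual data leave a country. The drawbacks are wider tables and a result that depends on the weights, which should therefore be fixed in the SAP.

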6.7.3.2. META-ANALYSIS OF COMPARATIVE ANALYSIS

Meta-analyses will combine the estimates of adjusted HRs across countries using the inverse-variance method. Log-transformed HRs and their standard errors will be collected to calculate pooled HR estimates using random-effects models. Pooled HRs and their 95% CI will be reported using forest plots. In a sensitivity analysis, pooled HRs will be estimated using fixed-effect models.

Between-study heterogeneity

Prior to conducting meta-analyses, heterogeneity across the countries in terms of study design and conduct will be assessed. Specifically, the variability in population characteristics (including data availability), in pre- and post- PS matching balance in baseline characteristics between cohorts, as well as in observed incidence rates will be examined. If needed, changes in study population selection criteria or other analysis parameters will be considered to reduce such heterogeneity.

Statistical heterogeneity between country-level estimates will be estimated using Higgins' and Thompson's I^2 [9] and the moment-based estimate of τ^2 .

Both I^2 and τ^2 are derived using Cochran's Q statistic defined as

$$Q = \sum_{k=1}^K w_k \left(\hat{\theta}_k - \frac{\sum_{k=1}^K w_k \hat{\theta}_k}{\sum_{k=1}^K w_k} \right)^2; w_k = \frac{1}{s_k^2}$$

where $\hat{\theta}_k$ denotes the log-transformed per-country HR estimate, s_k^2 its variance, w_k the corresponding weight from the country-level study k calculated as the inverse of variance s_k^2 .

I^2 statistic

I^2 is the percentage of variability in the treatment estimates which is attributable to heterogeneity between studies rather than to sampling error. I^2 is formulated as

$$I^2 = \max \left\{ 0, 1 - \frac{Q - K - 1}{Q} \right\}$$

where Q is Cochran's Q statistic and K is the number of the per-country studies.

I^2 and its 95% CIs are used to assess the importance of between study heterogeneity as follows:

- 0% to 40%: might not be important
- 30% to 60%: may represent moderate heterogeneity
- 50% to 90%: may represent substantial heterogeneity
- 75% to 100%: considerable heterogeneity

Proprietary confidential information © 2024 Boehringer Ingelheim International GmbH or one or more of its affiliated companies

I^2 is sensitive to the precision of the included studies, with higher I^2 associated with increased precision in individual studies.

τ^2 statistic

The τ^2 statistic represents the variance of the distribution of the true effect-sizes. τ^2 will be calculated using the DerSimonian and Laird estimate:

$$\hat{\tau}^2 = \max \left\{ 0, \frac{Q-(K-1)}{\sum_{k=1}^K w_k - \frac{\sum_{k=1}^K w_k^2}{\sum_{k=1}^K w_k}} \right\}; w_k = \frac{1}{s_k^2}$$

where w_k denotes the corresponding weight from the per-country study k , and s_k^2 is the variance of HR estimate of per-country study k .

τ^2 is insensitive to the number of studies or to their precision but can be difficult to interpret. It is however expressed at the same scale as square of the effect size; hence its 95% CI represents the estimated range of true effect sizes.

Random-effects model

The random-effects model considers the observed per-country effect sizes as randomly sampled from a distribution of true effect sizes. The pooled effect size estimated by the model represents the mean of this distribution of true effect sizes.

In addition to the sampling error (squared as variance s_k^2), the random-effects model takes into account the variance of the distribution of the true effects, which is estimated as between-study heterogeneity tau-squared τ^2 . The weight w_k for each country k is calculated with τ^2 as an additional scaling factor, resulting in the adjusted random-effects weights w_k^* .

$$w_k^* = \frac{1}{s_k^2 + \tau^2}$$

The pooled HR estimate $\hat{\theta}$ is calculated using adjusted weights w_k^* .

[figure not shown]
$$\hat{\theta} = \frac{\sum_{k=1}^K \hat{\theta}_k w_k^*}{\sum_{k=1}^K w_k^*}$$

For each meta-analysis, pooled and country-level results will be presented in forest plots similar to Figure 8 showing the following items:

[figure not shown]
- Country identifier
- Number of events (IR/1000 person years) per study group
- HR and 95% CI for each country (on log scale)
- The weight (%) assigned to each country
- The estimated pooled HR and its 95% CI using a random-effect models (on log scale)

Proprietary confidential information © 2024 Boehringer Ingelheim International GmbH or one or more of its affiliated companies

[figure not shown]
- Total number of patients per study group
- Average follow-up time in person years
- Between-study heterogeneity τ^2 and its 95% CI
- The I^2 statistics and its 95% CI

[figure not shown]
Proprietary confidential information © 2024 Boehringer Ingelheim International GmbH or one or more of its affiliated companies

[figure not shown]
Proprietary confidential information © 2024 Boehringer Ingelheim International GmbH or one or more of its affiliated companies

[figure not shown]

Proprietary confidential information © 2024 Boehringer Ingelheim International GmbH or one or more of its affiliated companies

[figure not shown]

Proprietary confidential information © 2024 Boehringer Ingelheim International GmbH or one or more of its affiliated companies

Proprietary confidential information © 2024 Boehringer Ingelheim International GmbH or one or more of its affiliated companies

